During the application of NMES the force decreases. Some authors claim that the magnitude of fatigue is influenced by pulse width, frequency and intensity of electro-stimulation. As frequency is increased, the MEIC increases as well, which in turn increases metabolic consumption, thus generating fatigue (31).

Several authors have studied the effect of electro-stimulation with surface electrodes on fatigue, finding that medium frequency currents generate more fatigue than low frequency ones (5, 20).

There are various experimental models to study peripheral fatigue, but the one most used consists of applying electrical stimulation, reducing the central component (31).

There is no doubt that Laufer was one of the authors who researched on electro-stimulation-induced fatigue the most. To this end, she used a protocol which starts by measuring the MVIC to normalize the data. Then, she measures the MEIC during 21 repetitions, considering the first contraction as a hundred percent and the following contractions as a percentage of the first one (17). The next step is counting the number of contractions that were equal to or less than 50% of the initial strength, thus determining which current is more fatiguing (20).

Another option for calculating this variable is the determination of the Fatigue Index (FI), which consists of describing the percentage of reduction of the force induced between the first phase

(Pinit) and last phase (Pfinal), where a higher value indicates less fatigue and an FI = 1 implies that no fatigue has occurred. This formula is: FI=1-(Pinit-Pfinal)/Pinit (44).

OBJECTIVES

General

1. To compare induced isometric force, tolerance and fatigue in healthy subjects from 18 to 30 years of age, with Neo-Russian, Aussie and RBS currents, in the period from 11-30-2017 to 12-30-2017.

Specific

- 1.1. To evaluate the isometric force induced by Neo-Russian, Aussie and RBS currents by means of isometric dynamometry in healthy subjects from 18 to 30 years of age.
- 1.2. To compare the isometric force induced in healthy subjects aged 18 to 30 years by the different currents in order to determine which one induces greater force.
- 1.3. To evaluate the tolerance of Neo-Russian, Aussie and RBS currents using the Pain Visual Analogue Scale (VAS) in healthy subjects from 18 to 30 years of age.
- 1.4. To compare tolerance in healthy subjects aged 18-30 years to the three types of current in order to determine which one is less unpleasant.

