- 1.5. To evaluate fatigue upon application of Neo-Russian, Aussie and RBS currents by means of a fatigue test with isometric dynamometry in healthy subjects from 18 to 30 years of age.
- 1.6. To compare the fatigue induced by the different currents in healthy subjects between 18 and 30 years of age in order to determine which of the three produces less fatigue.

MATERIALS AND METHODS

a. Design type

Experimental, crossover, randomized study (45).

b. Location

The data collection was carried out in the "*[name] Terapia Física Especializada*" Center, located at [name], in the Autonomous City of Buenos Aires, Argentina, in the period from 11-30-2017 to 12-30-2017.

c. Universe

Students pursuing a degree in Kinesiology and Physiatry at the Instituto Universitario de Ciencias de la Salud Fundación H.A. Barceló (Autonomous City of Buenos Aires, Argentina), at Universidad Maimónides (Autonomous City of Buenos Aires, Argentina) and at the Universidad Nacional Arturo Jauretche (Florencio Varela, Buenos Aires, Argentina).

d. Population

Composed of 255 individuals, male (5, 41, 46), students pursuing a degree in Kinesiology and Physiatry at the Instituto Universitario de Ciencias de la Salud Fundación H.A. Barceló (Autonomous City of Buenos Aires, Argentina), at Universidad Maimónides (Autonomous City of Buenos Aires, Argentina) and at the Universidad Nacional Arturo Jauretche (Florencio Varela, Buenos Aires, Argentina).

e. Sample

Composed of 30 individuals according to the sample size estimate.

f. Sample size

To determine the required sample size, a pilot test was carried out prior to the study, in which the 3 types of electrical stimulation were randomly applied to 5 subjects. In order to estimate the variability of the sample, the global standard deviation of the 15 measurements was considered (SD=19.58%). A sample size for a Two-tailed T-Test was estimated, assuming an alpha error of 0.05, a power of 0.8 and a delta of 10%. For a crossover design only 1/2 of the calculated sample size is required, since the same subject contributes to all 3 groups. This results in a sample size of 30 subjects (47). The distribution coefficient was 1:1. (48)

g. Sampling:

Consecutive non-probability.

h. Criteria

a. Inclusion: Available, healthy, male volunteers between 18 and 30 years of age, with right-dominant lower limb, who are physically active (9, 41).

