To meet the specific objectives in 1.2, 1.4 and 1.6, an analysis of the variance of a repeated measurement factor was performed in order to determine the effect of three wave types (Aussie, NR and RBS) on the %MVIC, tolerance level and fatigue. Independent analyses were performed for each outcome variable. Bonferroni correction was applied for the *a posteriori* analyses, as appropriate. Results were expressed as mean difference and their respective 95% CI. The assumption of normality was evaluated using the Shapiro-Wilk test. The presence of outliers was determined by visual inspection of the box charts. The sphericity assumption was evaluated by means of the Mauchly test. When it was not possible to apply the parametric ANOVA test, the non-parametric Friedman test and the Wilcoxon test for Bonferroni-corrected samples were used for multiple comparisons.

To meet the specific objective in 1.2, it was analyzed which current shows the highest value of %MVIC (%MVIC-Neo-Russian vs. %MVIC-Aussie vs. %MVIC-RBS).

In order to comply with the specific objective in 1.4, it was analyzed to which of the currents the subjects referred a lower VAS value (VAS-Neo-Russian vs. VAS-Aussie vs. VAS-RBS) and which of the currents obtained a better ratio, calculated by using the formula mentioned above (Ratio-Neo-Russian vs. Ratio-Aussie vs. Ratio-RBS).

To meet the specific objective in 1.6, a comparison was made considering the number of repetitions $\leq 50\%$ of the initial value between the 3 different waves. No assumption of normality was made at any of the levels as assessed by the Shapiro-Wilk test ($p < 0.001$) for which the Friedman test was used for related samples. For post hoc comparisons the Wilcoxon Test for related samples was used with Bonferroni correction for multiple comparisons ($R \leq 50\%$ -Neo-Russian vs. $R \leq 50\%$ -Aussie vs. $R \leq 50\%$ -RBS). In addition, a comparison was made between %MVIC-F₁ vs. %MVIC -F₂₁ using the Wilcoxon Test for paired samples.

To compare fatigue rates between AU, RS and RBS groups, the Friedman non-parametric test was used with the Wilcoxon test for post hoc comparisons. Bonferroni correction was applied for post-hoc comparisons.

SOURCES AND INSTRUMENTS

- Notebook with Windows, Microsoft Office 2016 package, SPSS 22, Endnote X7.
- Owon PC-based oscilloscope, model VDS2062 60MHz and 100MHz bandwidth.

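### The stated power of 0.8 is for one unadjusted comparison at an unstated within-subject correlation of about 0.5; it is not shown for the Bonferroni-corrected pairs that answer objective 1.2

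*Combined protocol and SAP*

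**What the plan says.** Section f of Materials and Methods bases the size on a five-subject pilot in which each subject received all three currents. For variability, "the global standard deviation of the 15 measurements was considered (SD=19.58" (in per cent). The calculation is for a single two-group comparison: "A sample size for a Two-tailed T-Test was estimated", "assuming an alpha error of 0.05, a power of 0.8 and a delta of 10" per cent. The result is then halved: "For a crossover design only 1/2 of the calculated sample size is required, since the same subject contributes to all 3 groups". The answer is 30 subjects. The section does not name the outcome to which the SD and delta belong. It gives no within-subject correlation, within-subject SD or SD of paired differences, and no multiplicity adjustment.

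Specific objective 1.2 is to compare the force induced "by the different currents in order to determine which one induces greater force". In section n (Statistical processing of data), "an analysis of the variance of a repeated measurement factor was performed" for each outcome, and "Bonferroni correction was applied for the *a posteriori* analyses, as appropriate". For objective 1.2, "it was analyzed which current shows the highest value of %MVIC (%MVIC-Neo-Russian vs. %MVIC-Aussie vs. %MVIC-RBS"; that is, all three currents are set against each other. Friedman and Bonferroni-corrected Wilcoxon tests are the fallback. No power is given for any of these analyses.

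**The concern.** Two things separate the stated 0.8 from the analysis that identifies the best current.

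First, the reason given for halving is incomplete. Letting one subject serve in both groups turns about 120 measurements into about 60 subjects. The further step to 30 depends on how strongly a subject's results under different currents correlate, and the plan is silent on that. A global SD over 15 values mixes between-subject, within-subject and between-current variation, so it cannot supply the correlation.

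Second, the sizing alpha is 0.05 for one test, while the comparisons that say which current is better are Bonferroni-corrected.

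The practical risk lies in interpretation. A reader who meets a non-significant pairwise force result may take 0.8 as the chance that a 10-point difference would have been detected. That figure belongs to a different test under an undisclosed assumption.

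**Working it through.** **Inputs.** From section f: SD 19.58, delta 10, two-sided alpha 0.05, power 0.8, n = 30. From section n: Bonferroni correction; if all three pairs are tested, alpha per pair is 0.05/3 = 0.0167. Assumptions: SD and delta are absolute %MVIC points; the SD and correlation are the same for all currents and pairs; every rho below is assumed, since the documents give none.

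**1. The plan's figure.** n per group = 2 × (1.960 + 0.842)² × 19.58² / 10² = 60.2. Half is 30.1, which matches 30. The exact t version gives 62 per group, half 31. A one-sided test (48, half 24) and half of the two-group total (61) do not match, so it is the per-group figure that was halved.

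**2. What halving assumes.** SD of a paired difference = SD × √(2(1 − rho)), so paired n = 60.2 × (1 − rho).
- rho 0: 60.2 subjects.
- rho 0.5: 30.1 subjects.
- n = 30 exactly: rho = 1 − 30/60.18 = 0.50.

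**3. Power for one given pair at n = 30, rho 0.5.** SD of differences = 19.58; 10 / (19.58/√30) = 2.80.
- Normal, alpha 0.05: Φ(2.80 − 1.96) = 0.80.
- Normal, alpha 0.0167: Φ(2.80 − 2.39) = 0.66.
- Exact paired t: 0.77 at 0.05 and 0.60 at 0.0167.

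**4. Over a range of rho (exact paired t, n = 30).**

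| Assumed rho | SD of differences | Power, alpha 0.05 | Power, alpha 0.05/3 | Difference detectable with 80% power, alpha 0.05/3 |
|---|---|---|---|---|
| 0.3 | 23.17 | 63% | 44% | 14.4 |
| 0.5 | 19.58 | 77% | 60% | 12.2 |
| 0.7 | 15.17 | 94% | 85% | 9.4 |
| 0.8 | 12.38 | 99% | 96% | 7.7 |

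The last column scales with the SD of differences; at rho 0.8 it is 12.17 × 12.38/19.58 = 7.7. By exact t, 80% power needs rho of at least 0.534 at alpha 0.05 and 0.663 at 0.05/3 (0.626 by the normal approximation).

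**5. The ANOVA and the full question, rho 0.5.** The omnibus test has 2 and 58 df and noncentrality 30 × Σ(mean − grand mean)² / (19.58² × (1 − rho)), assuming sphericity.
- Means 0/0/10: 2000/191.7 = 10.4, power 81%.
- Means 0/5/10: 1500/191.7 = 7.8, power 68%.
- By simulation for means 0/0/10, the best current beats both others after correction in about 44% of trials; at least one corrected pair is significant in about 77%.

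For comparison, omnibus power for the two patterns is 66% and 53% at rho 0.3, and 96% and 89% at rho 0.7.

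**The case against.** The strongest reply is that the correlation may well be high. Under section l, all three currents are measured in one visit, in the same position, and divided by the same subject's MVIC. At rho 0.7 or 0.8 the corrected pairs have 85% or 96% power. This stands. A reader might infer from the figures at rho 0.5 that the trial is underpowered, and the documents do not support that: they give no correlation, so they show neither adequate nor inadequate power for the corrected pairs.

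A second reply is that the ANOVA at 0.05 is the first test for objective 1.2 and keeps 81% power for means 0/0/10 at rho 0.5. That also stands, so 0.8 is roughly right for more than one unadjusted comparison. It is not right for 0/5/10 (68%), and the omnibus test cannot say which current is best.

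Third, section n plans mean differences with 95% confidence intervals, which show what a non-significant result leaves open better than any planning power does. This protects the reader on the parametric route. The plan does not say the same for the Friedman and Wilcoxon fallback.

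Finally, the text is in the past tense and the sample is fixed, so no power statement can change the design. That limits the remedy to wording. It does not make the present wording accurate.

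**Conclusion.** The point holds as a gap in what the stated power covers. The 30 is arithmetically reproducible, but its 0.8 refers to one unadjusted paired comparison at a within-subject correlation of about 0.5, and the reason given for halving supports about 60 subjects without that correlation. On the plan's own implied inputs, power for a given Bonferroni-corrected pair is 60% by exact t against 77% unadjusted, or 66% against 80% by the normal approximation.

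These sizes rest on three assumptions: that SD and delta are %MVIC points, that all three pairs are tested, and the chosen rho. The omission itself depends on none of them and is certain. The direction and size of any shortfall are not: at rho of about 0.663 or more, 80% per corrected pair is met. The paired-t figures do not cover the Wilcoxon fallback.

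**What to change.** Keep n = 30 and every planned test, and leave the calculation on record as the way 30 was chosen. In section f:

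- Name the outcome and units of the SD and delta (presumably %MVIC points).
- State that the 1/2 rule assumes a within-subject correlation of 0.5.
- State that 0.8 refers to one unadjusted pairwise comparison.
- For the Bonferroni-corrected pairs, give a short range with rho labelled as an assumption: at rho 0.3 / 0.5 / 0.7 / 0.8, power of 44 / 60 / 85 / 96% and detectable differences of about 14.4 / 12.2 / 9.4 / 7.7 points.

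If the subject-level values are available, also report the within-subject residual SD. The pilot gives it on 8 df; the trial's own data give it more precisely, on 58 df if all 30 complete. Interpret non-significant pairs from the planned 95% confidence intervals, not from the 0.8.

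The cost is one reworded paragraph and a less favourable, wider power statement. No extra subjects are needed. The documents do not say whether the pilot values were kept, so that step is conditional.

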- b. Exclusion:** Having a right-dominant lower limb injury, skin lesions in the quadriceps area, having a pacemaker, cardiovascular or neurological diseases (18, 25). Subjects who have exercised 72 hours before the protocol (49, 50).
- c. Elimination:** Missing one or both appointments for evaluation, the patient's own decision to abandon the protocol while it is being carried out, intolerance to the procedure (51).

i. Randomization:

In order to minimize the potential bias of the order in which interventions are initiated (e.g., the effect of fatigue), the randomization sequence was generated prior to starting work (9, 23, 25, 52). The number 2 generator, available at <http://www.randomization.com/>, was used for situations where subjects must receive all interventions in random order, with balanced permutations, forming 5 x 6 blocks for the three currents of interest (53). The results of said distribution were as follows:

1. Aussie - RBS - Neo-Russian.
2. RBS - Neo-Russian – Aussie.
3. Aussie - Neo-Russian - RBS.
4. RBS – Aussie - Neo-Russian.
5. RBS - Neo-Russian – Aussie.
6. Aussie - RBS - Neo-Russian.
7. Aussie - Neo-Russian - RBS.
8. Aussie - Neo-Russian - RBS.
9. Neo-Russian – Aussie - RBS.
10. Neo-Russian – Aussie - RBS.
11. Aussie - RBS - Neo-Russian.
12. Neo-Russian – Aussie - RBS.
13. Neo-Russian - RBS – Aussie.
14. Aussie - Neo-Russian - RBS.
15. Neo-Russian - RBS – Aussie.
16. Neo-Russian - RBS – Aussie.
17. Aussie - RBS - Neo-Russian.
18. RBS - Aussie - Neo-Russian.
19. RBS - Aussie - Neo-Russian.
20. Aussie - RBS - Neo-Russian.

21. Neo-Russian – Aussie - RBS.
22. Neo-Russian - RBS – Aussie.
23. Neo-Russian - RBS – Aussie.
24. Neo-Russian – Aussie - RBS.
25. RBS - Aussie - Neo-Russian.
26. RBS - Neo-Russian – Aussie.
27. Aussie - Neo-Russian - RBS.
28. RBS - Aussie - Neo-Russian.
29. RBS - Neo-Russian – Aussie.
30. RBS - Neo-Russian – Aussie.

j. Blinding

The subject was blindfolded so that he would not watch the procedure. The study subject did not know the type of current applied and the operator was alien to the work and unaware of the hypothesis. The database was coded in order to conceal the interventions from the statistical analyst (25, 45).

k. Ethical aspects

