With each type of current, the intensity was increased until it reached the maximum tolerable by the subject, which situation was communicated to the operator (23, 25, 32, 52). Upon reaching said intensity, it was noted down accordingly, and then 3 contractions of 3 seconds duration were measured by isometric dynamometry, with a 120-second pause between them. Once the 3 contractions with the first current were measured, the second and then the third type of electro-stimulation followed, in the order as randomly determined (9, 23, 25, 52). An interval of 120 seconds was also taken between the determinations of the MEIC with each current, in order to minimize fatigue (9). The best of the 3 repetitions was considered (9, 23, 31, 52).

Whenever the third one was the best, additional measurements were taken until a decrease in torque was obtained in order to determine the maximum (56).

Work and rest times were controlled by a chronometer and also by the dynamometer software. The best of the three contractions and, when necessary, the request for additional repetitions to obtain the best one, was automatically determined by the software, which also served to store the data that was later transferred to an Excel 2016 table.

The following parameters were used to perform the MEIC tests (Table 1):

VARIABLE	NEO-RUSSIAN	AUSSIE	RBS
Emission mode	Synchronous	Synchronous	Synchronous
Waveform	Rectangular biphasic symmetrical	Sinusoidal	Rectangular biphasic symmetrical
Carrier frequency	2500 Hz	1000 Hz	-
Phase duration	200 us	500 us	200 us
Pulse width	400 us	1000 us	400 us
Modulation frequency	50 Hz	50 Hz	50 Hz
Duty cycle	50 %	20 %	-
Burst duration	10 ms.	4 ms.	-
Ramp-up	1 sec.	1 sec.	1 sec.
On time	3 sec.	3 sec.	3 sec.
Ramp-down	1 sec.	1 sec.	1 sec.
Rest time	120 sec.	120 sec.	120 sec.

Table 1: Parameters for electrical stimulation during MEIC measurement.

e. Normalizing MEIC data

In order to normalize the data, MEIC will be expressed as percentage of MVIC (% MVIC) (17, 20, 23, 52, 58). The calculation was done in an Excel 2016 table. The formula was the following:

$$\% \text{ MVIC} = (\text{MEIC} / \text{MVIC}) \times 100$$

f. Determining tolerance to each type of electrical stimulation

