After recording the MEIC with each current, the subject was given a VAS scale and was asked to indicate how unpleasant he found the electro-stimulation, with 0 (on the left) being "no pain" and 10 (on the right) the equivalent of "crying in pain". Numerical data from the VAS was transferred to a Microsoft® Excel® 2016 table (20, 21, 57, 59).

Although an uncomfortable stimulus may not necessarily generate less force, what is sought is balance between these variables (14). That is why, considering that a current is more effective for electro-stimulation the more force it induces and the less discomfort it generates, the coefficient between the % MVIC and the VAS was calculated, thus establishing the "ratio" value through the following formula:

$$\text{Ratio} = \% \text{ MVIC} / \text{VAS}$$

g. Measuring fatigue

The fatigue induced by the three types of electrical stimulation was measured after one week of washout period (20).

The same isometric dynamometer was used, positioning the subject as indicated above. (5, 9, 12, 23, 26, 31, 37-40).

The motor points were detected and two unused self-adhesive electrodes were placed on them (9, 22, 52, 57).

The patient was instructed to cross his arms over his chest and to relax (5). The subject was blindfolded to prevent him from watching the procedure. The studied subject did not know the order of the procedures applied and the evaluator was not aware of the working hypothesis, thus defining a double-blind study (25, 45). The measuring system was attached to the distal end of the right lower limb by means of an ankle brace (9).

The patient was asked not to make any voluntary contraction or collaborate in any way, but just let the electrical stimulation generate the contraction (20). The intensity was increased until it reached the maximum tolerable by the subject, which situation was communicated to the operator (23, 25, 32, 52). Data was taken from the MEIC of 21 contractions (20), consisting of 1 second of ramp-up, 3 seconds of contraction, 1 second of ramp-down (60) and 5 seconds of rest time. The dynamometer was configured to collect data for 320 seconds and then the peak values of each of the 21 contractions were manually reviewed and transferred to Microsoft® Excel® 2016.

This variable was identified as maximum voluntary isometric contraction in fatigue test (MEIC-F).

The following parameters were then used to perform the fatigue test (Table 2):

VARIABLE	NEO-RUSSIAN	AUSSIE	RBS

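### If elimination is applied study-wide, a subject lost only at the fatigue visit loses complete force, VAS and ratio data for no analytical reason

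*Combined protocol and SAP*

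**What the plan says.** Materials and Methods, section h (Criteria), lists Elimination separately from inclusion and exclusion. The first trigger is "Missing one or both appointments for evaluation". The others are the subject's "own decision to abandon the protocol while it is being carried out, intolerance to the procedure". None is tied to a particular visit or outcome, and the consequence for data already recorded is not stated.

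The procedures (section l) divide the outcomes between two sessions:

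- **First session, force.** With each current in turn, "the intensity was increased until it reached the maximum tolerable by the subject", and "then 3 contractions of 3 seconds duration were measured by isometric dynamometry, with a 120-second pause between them".
- **First session, tolerance.** "After recording the MEIC with each current, the subject was given a VAS scale". The ratio is then calculated from %MVIC and VAS.
- **Second session, fatigue.** "The fatigue induced by the three types of electrical stimulation was measured after one week of washout period". The test uses 21 contractions with 5 seconds of rest, again at the maximum tolerable intensity.

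Section n gives each outcome its own repeated-measures ANOVA, with Friedman and Wilcoxon tests as the fallback. It defines no analysis set and no handling of partial data. On size, section f states: "This results in a sample size of 30 subjects".

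**The concern.** Missing one appointment is enough to trigger elimination, so a man who completes the first session and misses the second is treated like a man who attended neither. The first has everything needed for objectives 1.1 to 1.4; the second has nothing. If elimination means removal from the data, only that wording keeps the first man out of the force, VAS and ratio analyses, because the planned tests would otherwise include him.

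Loss at the second visit is plausible because that session is the heavier one. It has 3 × 21 = 63 contractions with short rests, against at least 3 × 3 = 9 with 120-second rests at the first.

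At stake is precision for force and tolerance in a study of 30. The randomisation list has exactly 30 entries, five per sequence, and no replacement rule is stated. Each unreplaced removal therefore also unbalances the sequences.

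**Working it through.** **Which outcomes need the second visit**

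| Outcome | Objectives | Source | Needs visit 2? |
|---|---|---|---|
| Force (%MVIC) | 1.1, 1.2 | Visit 1, all three currents | No |
| VAS | 1.3, 1.4 | Visit 1, after each current | No |
| Ratio | analysed under 1.4 | %MVIC and VAS | No |
| Fatigue count and index | 1.5, 1.6 | Visit 2 | Yes |

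A subject lost only at visit 2 is complete on the first three rows. A subject who stops during visit 1 before all three currents are measured lacks a current, and drops out of the repeated-measures ANOVA or Friedman test under any rule. The point does not concern him.

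**The plan's own sample size.** Inputs from section f: SD 19.58, delta 10, two-sided alpha 0.05, power 0.80, result halved for the crossover.

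- Per group: 2 × [19.58 × (1.960 + 0.842) / 10]² = 60.18, rounded up to 61.
- Halved: 30.1 before rounding, 30.5 after. The stated 30 reproduces, with no allowance for losses.

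Halving amounts to taking the SD of the within-subject difference as 19.58, since 19.58 × √(2(1 − 0.5)) = 19.58. That is a within-subject correlation of 0.5.

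**Effect of avoidable losses on the force comparison.** The documents give no elimination count, so one to three losses without replacement are assumed.

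- Power = Φ(10 / (19.58/√n) − 1.96). For n = 30: Φ(2.797 − 1.96) = 0.799.
- 95% CI half-width = t(0.975, n − 1) × 19.58/√n. For n = 30: 2.045 × 3.575 = 7.31 points.

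| n | Power, normal approximation | Power, exact paired t | CI half-width | Widening |
|---|---|---|---|---|
| 30 | 79.9% | 77.2% | 7.31 | – |
| 29 | 78.5% | 75.7% | 7.45 | 1.9% |
| 28 | 77.1% | 74.1% | 7.59 | 3.8% |
| 27 | 75.6% | 72.4% | 7.75 | 5.9% |

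**Sensitivity.** With other assumed correlations, SD of the difference = 19.58 × √(2(1 − ρ)). Going from 30 to 27 subjects, power falls from 65.7% to 61.1% at ρ = 0.3 (4.6 points), and from 95.1% to 92.9% at ρ = 0.7 (2.2 points). At the Bonferroni level for three pairwise tests (0.05/3), it falls from 65.7% to 60.2% at ρ = 0.5. The low starting value there is a separate sample-size matter and is not caused by elimination.

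No VAS standard deviation is given, so the same calculation cannot be made for tolerance.

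**The case against.** The strongest reply is that the premise is unproved. Elimination sits among the eligibility criteria, the statistical section never mentions it, and the wording could mean only that participation ends. That stands in part: the meaning is open, and the point is conditional on it. But a man who has missed only the last visit has little participation left to end, so removal from the data remains the more natural reading. The flowchart is not visible in the reviewed text and cannot settle it.

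Second, one common set of subjects for all outcomes is defensible when the general objective covers force, tolerance and fatigue together. That is fair, but the plan does not give this reason, and it analyses each outcome separately.

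Third, the losses may be nil, or subjects may have been replaced from the population of 255. Both are possible; the documents give neither a count nor a replacement rule.

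Two stronger readings are tempting and are not supported:

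- **That removal for intolerance selects on a study outcome and biases objective 1.4** ("To compare tolerance in healthy subjects aged 18-30 years to the three types of current in order to determine which one is less unpleasant"). VAS is described only for the first session, the comparison is within subject, and removing a man removes all three of his scores. Bias in a between-current difference needs visit-2 elimination to be related to that man's own VAS differences. Nothing in the documents shows this.
- **That intolerance would go unreported.** No text says elimination counts are withheld, and section n provides for frequencies and percentages of categorical variables.

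**Conclusion.** The point holds in a limited form. Applied study-wide on its natural reading, the elimination rule needlessly drops complete data for objectives 1.1 to 1.4 when a subject is lost only at the fatigue visit. The documents do not show that any subject was in fact removed.

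The cost is modest: about 1.4 points of power for one such loss and 4.3 points for three (79.9 − 78.5 and 79.9 − 75.6). This rests on the plan's SD, delta and halving rule, on assumed loss counts, and on no replacement. The actual effect may be zero. It is a minor matter, worth correcting because the remedy is cheap.

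**What to change.** Apply elimination outcome by outcome. Analyse each outcome on all randomised subjects who have data for all three currents on that outcome, except where consent to use of data was withdrawn. Give n for each outcome, and report eliminations by reason, visit and current.

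Data collection is described in the past tense, so the authors should state what was actually done. If subjects were removed study-wide, say so and present the outcome-specific analysis as a labelled re-analysis.

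The cost is a sentence or two of analysis wording and one disposition table, with no new subjects, visits or software. The drawback is that the analysed sets may differ slightly between outcomes, which the n per outcome makes visible. When stimulation is stopped for a subject is not in question here.
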